### **Purpose**

The goal of this research is to develop, refine, and pilot-test a mobile interpretation bias modification intervention to reduce cognitions that contribute to elevated suicide risk and to assess the impact of reductions in suicide cognitions and hostile interpretation bias on suicide risk and functioning.

### **Background and Significance**

According to the fluid vulnerability theory, suicide risk fluctuates as a function of chronic and acute vulnerability factors. One of the factors that contributes to persistent vulnerability is what is known as a “suicidal belief system”. This belief system is made up of several well-studied, cognitive constructs, such as hopelessness, thwarted belongingness, perceived burdensomeness unlovability, unbearability, and unsolvability. Each of these constructs have been associated with suicide-related outcomes. For example, suicide cognitions have been prospectively associated with subsequent suicide attempts among military personnel. In another study, suicide cognitions were stronger predictors of future suicide attempts than current suicidal ideation or prior suicide attempts. In fact, thwarted belongingness, unlovability, and unbearability were uniquely related to prospective attempts over a two-year period, above and beyond other well-established risk factors. Suicide cognitions are conceptualized as enduring, chronic vulnerability factors that predispose individuals to suicidal crises. Therefore, modification of these beliefs may reduce suicidal thoughts and behaviors.

In addition to suicide cognitions, another potentially modifiable risk factor for suicide is anger. Recent research (including from our team) has demonstrated a strong, consistent relationship between anger and suicidal thoughts and behaviors in civilian and veteran samples. For example, in a longitudinal, nationally-representative sample, anger was prospectively associated with subsequent suicidal ideation and attempts, even after adjusting for well-established risk factors.

Interpretation bias modification techniques have been used in recent years to modify cognitive biases that cause and maintain psychiatric disorders. Interpretation bias modification is delivered *via* computer, tablet, or smart phone and essentially helps participants to adopt more adaptive interpretational styles through repeated practice. [name] has developed an app to deliver her hostile interpretation bias modification intervention with ~10 minute treatment session delivered 5-7 times per week for 4 weeks. The current project will use this paradigm to develop a similar intervention to reduce suicidal cognitions for Veterans. The impact of this intervention as well as the hostile interpretation bias intervention on suicide risk and daily functioning will be examined.

## Aims

**Aim 1(a). Develop a mobile interpretation bias modification intervention entitled Mobile Intervention for Suicidal Thoughts (MIST) to reduce cognitions that contribute to elevated suicide risk.** We will develop content to target cognitive factors that contribute to suicide risk and program this content into a mobile application similar to an existing app developed by the team to target hostile interpretation bias, entitled MIRA.

**Aim 1(b). Use a successive cohort design to refine the MIST intervention among Veterans with PTSD, problematic anger, and elevated suicidal ideation.** To refine the intervention developed in Aim 1(a), the app will be tested in two cohorts (each  $n = 5$ ) of Veterans with problematic anger, and suicidal ideation. After each cohort uses the MIST application for four weeks, a quantitative and qualitative evaluation will be conducted with each Veteran. Revisions will be conducted before the next cohort is treated. Then, a third cohort ( $n = 4$ ) will be recruited to test a web-based version of the MIST intervention delivered via Qualtrics.

**Aim 2. Assess the impact of reductions in suicide cognitions and hostile interpretation bias on suicide risk and functioning.** After using the MIST intervention for four weeks, participants will use the MARI intervention for another four weeks. For the duration of the study (all eight weeks of treatment), EMA data will be collected to evaluate the impact of both interventions on suicide risk and daily functioning.

## Design

The proposed research project has two aims: 1) to develop and refine the MIST mobile intervention; and 2) to assess the impact of reductions in suicide cognitions and hostile interpretation bias on suicide risk and functioning among Veterans with problematic anger, and elevated suicidal ideation. The project has been designed in order to complete both aims simultaneously. The first step is to develop training scenarios for the MIST intervention. [name] has already started developing these scenarios to fit into specific themes of types of cognitions that have been theoretically and empirically linked to suicide: unbearability (*I can't tolerate being this upset*), unlovability (*I am unworthy of love*), unsolvability (*Nothing can solve my problems*), thwarted belongingness (*I do not belong*), perceived burdensomeness (*Others are better off without me*), and hopelessness about the future (*Things will not improve*). Unique scenarios will be developed for 28 treatment sessions (daily sessions for four weeks). When the scenarios have been developed, they will be reviewed by a team of experts (i.e., doctoral level psychologists with experience working with this Veteran population) who will rate them on how relevant they are for the Veteran population. They will also share comments and suggestions for refining these scenarios. Each scenario will be reviewed by at least one expert. Scenarios with low relevance will be revised before inclusion in the app. These are the same procedures used to develop the content for the MARI app.

In order to refine the MIST mobile intervention, a successive cohort design will be used. Successive cohort design utilizes an iterative process for by which psychosocial treatments in the early stages of development are systematically refined and modified. Qualitative and quantitative data collected by providing the treatment to these small

## Mobile Intervention for Suicide Cognitions

cohorts is used to inform these revisions. Accordingly, we will be refining the treatment approach with two successive cohorts of  $n= 5$  Veterans with problematic anger, and elevated suicide risk. After the first cohort uses the application, a qualitative and quantitative evaluation will be conducted. Revisions will then be made based on these evaluations before another cohort of  $n = 5$  Veterans is treated. Again, following treatment an evaluation will be completed and further revisions will be made to the treatment. This same method was used successfully to develop the MARI app.

Following completion of the second cohort, we will be testing a third cohort ( $n=4$ ) using the web-based version of the MIST intervention delivered via Qualtrics. This intervention will include the same MIST treatment scenarios and EMA questionnaires delivered via Qualtrics links directly to the Veterans' phones.

**Procedures:** All study procedures can be completed remotely using video conferencing services and mailings to minimize potential COVID-19 exposure. Participant will provide informed consent and HIPAA authorization via mail or with DocuSign where available. At an initial assessment, after establishing that they meet study criteria, they will complete a battery of baseline self-report questionnaires. They will then be instructed on how to complete the MIST treatment sessions and diary entries via their phone through Qualtrics. Four weeks later, each participant will complete a post-MIST interview during which they will provide detailed feedback on their experience using the MIST intervention and some self-report questionnaires. These semi-structured interviews will assess how helpful they found the intervention. They will be asked to elaborate upon what aspects of the intervention they think are most and least helpful and to provide suggestions on how it could be improved. They will also be shown a list of 100 random MIST treatment scenarios and asked to provide feedback and suggestions on the content and wording of these scenarios.

They will then be instructed to complete the MARI treatment sessions and diary entries via Qualtrics for another period of four weeks.

Following the completion of each cohort, quantitative and qualitative data will be analyzed. Based upon results, the intervention structure and content will be revised. The content that will be subject to revisions includes IBM content (e.g., topics and themes of scenarios). After the final cohort is completed, the MIST intervention will be finalized.

**Measures:** The following self-report measures will be administered at pre-treatment, post-MIST, and post-MARI assessments: *suicide cognitions* will be assessed with the Suicide Cognitions Scale, Beck Hopelessness Scale, Interpersonal Needs Questionnaire; *hostile interpretation bias* will be assessed with the Word Sentence Association Paradigm-Hostility; *suicide risk* will be assessed with the C-SSRS and the Beck Scale for Suicidal Ideation; *anger* will be assessed with the Dimensions of Anger Reactions; *functioning and quality of life* will be assessed with the Brief Inventory of Psychosocial Functioning (IPF) and WHOQOL-BREF. Participants will also complete the PTSD Checklist for DSM-5, the Patient Health Questionnaire-9, and a

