**Figure 7. Example of a Training Scenario in MIRA App**

We will be delivering the intervention daily for 4 weeks. It will include 28 treatments sessions that will each take approximately 10 minutes to complete. Each session will include 42 training scenarios. No scenario will be

repeated across these sessions. To this end, 1,176 unique training scenarios have been developed. Scenarios have been reviewed by 9 PTSD experts in the field and

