### *MIST Intervention*

The MIST intervention will be identical to the MARI intervention. The only difference is that the treatment sessions will include the scenarios that are being developed (see Design section) to target suicide cognitions. For example, "You make a mistake." Next, another sentence appears that offers a resolution to the scenario that is incompatible with the suicide cognition being targeted (in this example, unsolvability). The sentence following this particular scenario reads, "It can be fi\_ed." The participants fill in the missing letter of the word, forming the word "fixed," and resolving the scenario in a way to change the targeted suicidal cognition. This is then reinforced by requiring the participants to correctly answer "yes" or "no" to a comprehension question (i.e., "Are things permanently damaged?"). In this example, they must answer "no" to proceed.

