## Data Analysis and Statistical Considerations

Rapid turn-around analysis of the qualitative interviews will be conducted according to methods described by Hamilton. Participant impressions of the MIST app, feedback on the content of the scenarios, usability of the app, perceived strengths and weaknesses, and suggestions for improvement will be compiled and used to make modifications to the app content and design.

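### Do the randomly drawn lists of 100 MIST scenarios leave too much of the scenario bank without Veteran review?

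*Combined protocol and SAP*

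**What the plan says.** The Procedures paragraph of the Design section states that "each participant will complete a post-MIST interview during which they will provide detailed feedback" on their experience with MIST. Of the same visit it says: "They will also be shown a list of 100 random MIST treatment scenarios and asked to provide feedback and suggestions". The comments are to cover content and wording. Costs and/or Payments to Subjects sets $25 for the task. No section says whether the list is common to all, drawn separately for each person, or dealt without overlap.

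The size of the MIST bank is not printed. The Design section plans 28 MIST sessions with unique scenarios. The MARI Intervention section says "Each session will include 42 training scenarios" and gives a MARI total of 1,176. The MIST Intervention section says "The MIST intervention will be identical to the MARI intervention" apart from scenario content.

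Before any participant sees the material, the Design section provides that "Each scenario will be reviewed by at least one expert", and scenarios of low relevance are revised before inclusion. Content is then revised after each cohort, with topics and themes given as the example of what may change. "After the final cohort is completed, the MIST intervention will be finalized". Data Analysis and Statistical Considerations lists "feedback on the content of the scenarios" among several qualitative inputs to those revisions.

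**The concern.** The lists are the only scenario-by-scenario Veteran comment that the plan describes, and they feed the refinement that Aim 1(b) is about. Fourteen participants reading 100 scenarios each make 1,400 readings, more than the 1,176 scenarios inferred for MIST. Every scenario could therefore be read by a Veteran within the effort already paid for. Independent draws would instead spend part of that effort on chance repeats and leave more than a quarter of the bank unread at item level when MIST is finalised. A common list would leave far more. Dealing one shuffled bank without overlap appears to remove the gap with no extra participant time or payment.

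**Working it through.** **Inputs.** 100 scenarios per list (Design, Procedures); cohorts of 5, 5 and 4, total 14 (Aims; Selection of Subjects); 28 sessions (Design); 42 scenarios per session (MARI Intervention). Dropout before the post-MIST visit is not stated, so smaller numbers of reviewers are shown too.

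**Bank size.** 28 x 42 = 1,176, which reproduces the MARI figure. Using it for MIST is an inference.

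**Coverage.** The chance that a given scenario is on a given list is p = 100/1176 = 0.0850. With n independent lists, the expected share on no list is (1 - p)^n. With lists dealt without overlap, the number on no list is max(0, 1176 - 100n).

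| Reviewers n | Independent: on no list | Dealt: on no list |
|---|---|---|
| 5 | 64.1% (754) | 57.5% (676) |
| 10 | 41.1% (484) | 15.0% (176) |
| 11 | 37.6% (442) | 6.5% (76) |
| 12 | 34.4% (405) | 0 |
| 14 | 28.8% (339) | 0 |

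One common list would leave 1 - p = 91.5% (1,076) unread at item level. If the bank held 1,000 or 1,400 scenarios, the independent figure at n = 14 would be (1 - 100/1000)^14 = 22.9% or (1 - 100/1400)^14 = 35.4%. The coverage arithmetic is therefore sound.

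**What dealing gives up.** The 1,400 readings are the same under either scheme; only their allocation changes.

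- Independent draws reach 1176 - 339 = 837 different scenarios, so 1400 - 837 = 563 readings are repeats. Dealing reaches all 1,176, with 1400 - 1176 = 224 repeats.
- Under independent draws the number of readers per scenario is Binomial(14, 0.0850). Two or more readers: 0.337 x 1176, about 396 scenarios. Three or more: 0.110 x 1176, about 130.
- Under dealing, at most 224 scenarios have two or more readers, and at least 1176 - 224 = 952 (81%) have exactly one.
- Scenarios listed in both cohort 1 and cohort 2: independent, (1 - 0.641)^2 x 1176 = about 151; dealt, 0. Cohorts 1 and 2 use the first 1,000 dealt scenarios. The 400 readings of cohort 3 then cover the last 176 and leave 224 for re-checks.

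**What a random 100 provides.** The Design section names six cognitive themes. If they are of equal size (an assumption), each reader sees about 100/6 = 17 scenarios per theme, and a cohort of five gives about 83 readings per theme. That is a reasonable sample for judging themes and style of wording.

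**The standard.** A shortfall needs a target. The Design section sets one for experts, namely every scenario, and sets none for item-level Veteran comment. It asks for a random sample. The 28.8% describes a consequence of sampling; it does not measure a failure to meet anything that the plan promises.

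**The case for a change.** The strongest case is that breadth costs nothing here and the team itself values such review. The MARI scenarios were reviewed both by experts and by people with PTSD, whereas the review of MIST scenarios before inclusion names only doctoral-level psychologists. Expert relevance ratings are also not Veteran comment on wording, and topics and themes are only an example of what may be revised, so item-level editing is plainly possible. With 1,400 readings available for 1,176 scenarios, full coverage is within reach.

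Much of this stands as fact, but it does not make dealing the better design. A successive cohort design works by review, revision and renewed evaluation, and dealing ensures that no scenario commented on in cohort 1 is listed again in cohort 2. With one reader, a weak scenario cannot be told apart from one person's taste. Risk/Benefit Assessment lets participants decline any question, so an item skipped by its only reader is lost, and the zero in the table is a best case. Scenarios rewritten between cohorts are also new text that earlier readers have not seen.

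The scenarios missing from every list are not unseen either. Participants are assigned all 28 sessions, must complete the word and answer the comprehension question for each scenario, and are then interviewed on what helped most and least.

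What does stand is that the plan does not say how the lists are drawn. A sentence would settle it, and a common list would give much narrower item-level coverage than either alternative. This is operational detail of a qualitative task in a 14-person pilot, and a working procedure can hold it.

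**Conclusion.** The concern does not hold. The figure of 28.8% (about 339 of 1,176) is correct if MIST has as many scenarios as MARI, all 14 participants review a list, and lists are drawn independently. The plan confirms the first only by inference and is silent on the third. More important, the figure is measured against full item-level Veteran coverage, a goal that the plan does not set. Lists without overlap exchange depth and re-checking for breadth: 81% or more of scenarios with a single reader, about 396 falling to at most 224 with two or more, and about 151 falling to zero on lists in both of the first two cohorts. Statisticians could reasonably prefer either. The choice affects content refinement only. The primary outcomes are feasibility and acceptability, described without efficacy testing, and no power, error rate or safety process depends on how the lists are drawn.

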## Mobile Intervention for Suicide Cognitions

brief questionnaire to assess their self-efficacy at managing suicidal thoughts and anger. On a 1-5 Likert scale they will be asked to rate: “how confident are you with your ability to cope with suicidal thoughts?” and “how confident are you with your ability to cope with anger?”. At the post-MIST and post-MIRA assessments, they will complete the Client Satisfaction Questionnaire.

EMA assessments will also be conducted for the duration of the time that participants are engaged in the MIST and MARI interventions (8 weeks). There will be one random alarm-prompted diary entry during the day and a nightly diary using established procedures from our team. The EMA diary will include assessments of: *suicidal ideation*; and *functioning and health related quality of life* using the brief IPF and items from the WHOQOL-BREF. EMA entries will also ask about affect and alcohol and substance use.

Demographics and Background Measures	Time (min)	Baseline	Post-MIST	Post-MIRA
Demographics	2	•		
Traumatic Life Events Questionnaire (TLEQ)	10	•		
Diagnostic Interviews				
Structured Clinical Interview for DSM-5	60	•		
Feasibility and Acceptability Measures				
Participant Recruitment	--	•		
Treatment Retention	--		•	•
Withdrawals	--	•	•	•
App Utilization	--		•	•
Client Satisfaction Questionnaire (CSQ)	5		•	•
Post-MIST Interview	30		•	
Clinical Measures				
Interpersonal Needs Questionnaire (INQ)	5	•	•	•
Suicide Cognitions Scale (SCS)	5	•	•	•
Beck Hopelessness Scale	5	•	•	•
Word Sentence Association Paradigm-Hostility (WSAP-H)	10	•	•	•
Columbia-Suicide Severity Rating Scale	5	•	•	•
Beck Scale for Suicide Ideation	5	•	•	•
Dimensions of Anger Reactions (DAR)	5	•	•	•
Brief Inventory of Psychosocial Functioning	5	•	•	•
WHOQOL-BREF	5	•	•	•
Patient Health Questionnaire-9 (PHQ-9)	5	•	•	•
PTSD Checklist for DSM-5 (PCL-5)	10	•	•	•

### Mobile Device Use

Study participants will access the MIST, MARI, and EMA interventions and assessments using their personal mobile devices. They will receive Qualtrics links to access the treatment sessions and EMA diary entries. These data will be collected via the VA instance of Qualtrics.

### Risk/Benefit Assessment

## Mobile Intervention for Suicide Cognitions

Participation is completely voluntary and participants are informed that they are free to refuse to answer any items on the questionnaires or questions from the interview that they do not wish to answer. They are also informed that they are free to decline participation in any procedure and can withdraw from the study at any time. Regarding qualitative data, participants will be informed that all published results will be anonymized, including any mention of city/medical center/clinic to protect the identity of participants.

Potential risks will be minimized by carefully screening potential participants according to the inclusion/exclusion criteria, closely monitoring symptom levels, and following established laboratory procedures. To ensure confidentiality, all records will be identified by the participant's identification number, not by name. All raw hard copy data will be kept in a locked file cabinet in a locked room. Data files will be stored on secure, password-protected computers. Finally, all project staff will complete educational units required by the Durham VAHCS IRB.

While participants may benefit from using the mobile intervention, there are no guaranteed benefits to the individual participant and no immediate benefits of the proposed research to others. There are potential benefits to others from the information generated that potentially will be helpful in increasing reach of treatments to target suicidal ideation and anger and developing more effective interventions for Veterans with suicidal ideation, PTSD, and problematic anger. In our opinion, the anticipated benefits of this study outweigh the potential risks.

### Selection of Subjects

We will screen up to 30 participants for the project for a desired total sample size of 14.

Inclusion/Exclusion Criteria	
Veterans must meet all inclusion criteria:	Veterans who meet any one of the exclusion criteria will be excluded:

• Report a score of <math>\geq 12</math> on the 5-item Dimensions of Anger Reactions Scale

• Can read at least 6th grade level material

• Report a score of 1-3 (indicating ideation without intent) on the Columbia-Suicide Severity Rating Scale (C-SSRS)

• Are engaged in mental health treatment and regularly attending appointments with a provider (e.g., therapy, counseling, medication management) at least every 3 months.

	

• Currently in a period of active psychosis or mania.

• Current moderate or severe alcohol or substance use disorder, established via SCID-5*

• Current imminent suicide risk or homicidal ideation requiring immediate intervention.

\* SCID-5 interviews will be administered by trained lab personnel who have been trained using standardized training, which consists of review of interview manuals,

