## Mobile Intervention for Suicide Cognitions

interview) directly to the VA secured server (in lieu of videorecording with an external device). If telehealth visits are done using VA's instance of WebEx, audiorecordings will be done to the VA WebEx cloud and moved as soon as possible to the VA secured server. Questionnaires will be completed orally, by mail, and/or via MyHealthyVet.

We would like to ask participants to complete measures related to stress, trauma, and coping strategies during the pandemic. New participants will complete these measures at their first visit, and ongoing participants will complete them at their next study visit. We are adding the CAIR Pandemic Impact Questionnaire (Lang, 2020; [https://www.nlm.nih.gov/dr2/CAIR-PIQ\\_scoring.pdf](https://www.nlm.nih.gov/dr2/CAIR-PIQ_scoring.pdf)), and another measure, COVID Core Questions, with variables of interest. If a participant endorses any item marked with an asterisk on the COVID Core Questions measure, we will ask them to complete a PTSD Checklist 5 related to that specific event. Because these are temporary measures to be used only during the COVID-19 pandemic, we have not added them to the consent form. Instead, participants will be informed verbally re: the measures, and will be told that they can refuse to answer them.

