**Safety Concerns.** Study therapists will be informed that prior to beginning interviews participants will need to identify an emergency contact for the participant to be used only in true emergencies (e.g., medical crisis, high risk suicidal ideation). If any participant expresses suicidal or homicidal ideation (SI and HI, respectively), study staff will respond using a standard of practice that has been used successfully in our lab's past telehealth-based trials. The study staff member responsible for the call will be instructed to gather more information from the participant, including information about plan, means, intent, intended victim (in the case of HI) and history of suicidal and homicidal behavior. Any participant who expressed SI will be provided with the suicide hotline number. The participant will be informed that the PI may contact him/her to talk more about his/her SI or HI. The study coordinator will obtain current contact information for the participant and inform the PI, who will contact the participant as necessary to ensure participant safety. In cases of imminent homicidality or suicidality, which are not anticipated, we will seek guidance from the Psychiatric Emergency Clinic on best strategies for follow-up, which could include, but is not limited to, self-presentation at the VA's emergency room with the help of an emergency contact, calling 911, or calling local police for a wellness check.

**Study Communication.** For any participant who indicates that they are willing to receive study communications via email, we will use Azure to send secure communications to them re: appointment scheduling, missed appointments, etc. Content from the study's IRB-approved letters will be included in the emails.

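### The C-SSRS and the Beck Scale for Suicide Ideation are not exempt from mail or portal completion, although one decides entry and the plan's response to suicidal ideation is built on a live call

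*Combined protocol and SAP*

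**What the plan says.** All references are to the combined protocol and SAP.

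- **Entry.** Selection of Subjects requires Veterans to "Report a score of 1-3 (indicating ideation without intent) on the Columbia-Suicide Severity Rating Scale (C-SSRS"). It gives no mode, rater or date for that score. Trained administration is described only for the SCID-5. Current imminent suicide risk is a separate exclusion.
- **Type of measure.** The Measures paragraph opens "The following self-report measures will be administered at pre-treatment, post-MIST, and post-MARI assessments". Within that list, suicide risk "will be assessed with the C-SSRS" and with the Beck scale. The schedule table puts both under Clinical Measures, apart from Diagnostic Interviews, with 5 minutes each at baseline, post-MIST and post-MARI (the plan also writes post-MIRA).
- **Mode.** The Procedures paragraph says "All study procedures can be completed remotely using video conferencing services and mailings to minimize potential COVID-19 exposure". The COVID-19 Temporary Study Procedures make visits live by telehealth, with phone as back-up, and then say of questionnaires: "Questionnaires will be completed orally, by mail, and/or via MyHealthyVet".
- **Response.** Under Safety Concerns, when a participant expresses suicidal or homicidal ideation, "The study staff member responsible for the call will be instructed to gather more information from the participant", including about plan, means and intent. The coordinator then informs the principal investigator.
- **Order of events.** The Procedures paragraph has eligibility established at an initial assessment, then the baseline self-report battery, then instruction on MIST.

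**The concern.** Background and Significance adopts a theory in which "suicide risk fluctuates as a function of chronic and acute vulnerability factors". Risk/Benefit Assessment relies on careful screening and close symptom monitoring to limit harm. Both safeguards work only if a member of staff sees an answer about suicidal intent while it is still current.

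The mode rule treats all questionnaires alike, and the two suicide scales are classed among them. An answer indicating intent could therefore be on paper in the post or in a portal inbox, while the steps that follow such an answer are written for someone already speaking with the participant. At stake is the safety of a sample chosen for suicidal ideation. A second issue is how well the study can document that its entrants had ideation without intent.

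**Working it through.** The documents state no figure on this point and no formula applies. The check sets the sections side by side.

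1. **Are the two scales questionnaires under the plan's own classification?** Yes. Measures lists both as self-report, and the schedule table keeps them apart from Diagnostic Interviews. No rater is named for the C-SSRS.

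2. **May questionnaires be completed away from staff?** Yes. Oral, mail and portal completion are all allowed. The explicit rule is in a temporary section, but the main Procedures paragraph also allows mailings, and for all procedures.

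3. **Is either scale exempted?** No section does so.

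4. **Do live visits close the gap?** Not by themselves. The temporary procedures set the mode of visits and the mode of questionnaires in separate sentences, and the second still permits mail and portal.

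5. **Does the response procedure reach a mailed or portal form?** Only once the form is read. Expressing ideation on a form could count as the trigger, but the steps are given to the person handling a call. No section says who reads returned forms, or when. Data and Safety Monitoring lists participant contact, a toll-free number, weekly meetings and real-time monitoring of adverse events, but does not mention review of returned questionnaires.

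6. **What follows at each assessment?**
   - *Baseline.* The C-SSRS decides entry, which the Procedures paragraph places before the self-report battery. Yet Measures puts the C-SSRS in that battery, and the table has a single baseline column. The plan does not say whether the qualifying score and the battery score are the same, or that staff see it live.
   - *Post-MIST.* The visit includes an interview and some self-report questionnaires, and MARI instruction follows. Nothing requires the suicide scales to be read before that instruction.
   - *Post-MARI.* This is the last of up to three visits, so no later scheduled visit would bring an unread form to light.

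7. **How long could an answer go unseen?** The delay is the date staff read the form minus the date it was completed. For live completion it is essentially zero. For mail or portal, the documents give no turnaround and no review schedule, so the delay cannot be computed. Nor do they say how many forms would go that way.

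**The case against.** The strongest reply is that the plan already points to live contact. Eligibility is established before the questionnaire battery. No earlier screening visit is described, no study procedure may precede consent, and visits are live. Baseline includes a 60-minute SCID-5 interview. Imminent risk excludes a Veteran whatever the C-SSRS score, and staff ask about intent when ideation is expressed. The explicit mail and portal sentence is in a temporary section and names neither the C-SSRS nor screening. The study is also a pilot limited to feasibility and acceptability.

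Much of this stands. It defeats a stronger inference that a reader might draw: that a stale C-SSRS score will admit someone whom the criteria exclude. That inference needs an appreciable gap between the qualifying score and the first MIST session, and the documents describe none. Setting no maximum interval is missing detail and does not show that a gap occurs. The separate exclusion for imminent risk narrows the exposed group further, to a Veteran whose score has risen above 3 but who is not judged to be at imminent risk. It would also go too far to say that the study cannot characterise its sample, since both scales are scheduled at baseline.

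The reply does not answer the mode problem. Live visits do not make the questionnaires live while a separate sentence allows otherwise. The questions about intent are not tied to reading a returned form or to the eligibility decision. The post-MIST and post-MARI exposure does not depend on how entry is timed.

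**Conclusion.** The concern holds as a gap between stated rules. The two suicide scales fall under a mail and portal option that does not exempt them, and the response procedure assumes a live call. Intent reported on such a form at any of the three assessments can go unseen until the form is read, and the score that decides entry need not be seen live.

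This rests on two readings: that the questionnaires in the mode rule include the measures listed as self-report, and that silence about an exemption means there is none. Both are the natural reading, but neither is explicit. The documents do not show that any form has been or will be handled this way, and the Procedures paragraph suggests that eligibility is settled at the initial assessment.

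The rule as written covers all 14 planned participants at three assessments each. That describes its reach and predicts no number of failures. This is an inexpensive safety improvement and does not threaten the study's feasibility and acceptability conclusions.

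**What to change.** Reconcile Procedures, Measures, Selection of Subjects and the COVID-19 Temporary Study Procedures as follows:

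- Take the C-SSRS and the Beck Scale for Suicide Ideation out of the mail and portal option.
- State that both are completed with staff, or reviewed by staff live, during the scheduled baseline, post-MIST and post-MARI visits.
- State in Selection of Subjects that the eligibility C-SSRS is the one obtained at the live initial assessment.

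All other questionnaires can keep the mail and portal option. Whether to add a maximum interval to the first session, a repeat assessment or any other clinical rule is for the sponsor to decide; none is proposed here.

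The cost is a wording amendment. The schedule table already allows 5 minutes for each scale, so 5 + 5 = 10 minutes per visit, and the temporary procedures already make visits live. The one small loss is that these two scales can no longer be mailed for convenience.
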